9.6.3 Laboratory Test Results

Chemistry, Hematology and Coagulation

Actual values and change from baseline for selected chemistry and hematology parameters will be summarized descriptively for each scheduled visit based on the safety analysis set.

Chemistry	Hematology	Coagulation
Total bilirubin	ANC	PT or INR
ALT (SGPT)	Hemoglobin	APTT
AST (SGOT)	Platelets	
Alkaline phosphatase	WBC	
Creatinine	Lymphocyte	
Phosphate		
Calcium (Corrected)		
Potassium		
Sodium		
Albumin		
Glucose		
Amylase		
Lipase		

Shift tables will be presented for the baseline toxicity grade by the worst on-study toxicity grade in a table form for selected parameters mentioned above if applicable. CTCAE version 5.0 will be used for toxicity grading for the above mentioned parameters excluding Total bilirubin, ALT (SGPT), AST (SGOT) and Alkaline phosphatase (CTCAE version 4.03 will be used for toxicity grading).

Potential Hy's law cases may be summarized.

9.6.4 Vital Signs

[figure not shown]
The analyses of vital signs include summary statistics over time and/or changes from baseline over time.

9.6.5 Physical Measurements

The analyses of physical measurements will include summary statistics at baseline.

9.6.6 Electrocardiogram

Summaries over time and/or changes from baseline over time will be provided for all ECG parameters. Subjects' maximum post baseline values will be categorized and the number and percentage of subjects in each group will be summarized.

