**4. Objectives, Endpoints and Hypotheses**

**4.1 Objectives and Endpoints**

Objectives	Endpoints
Phase 1b	
Primary	

 
Establish the safety and tolerability of AMG 420 at dose levels of 400 µg/day and 600 µg/day in subjects with relapsed and/or refractory multiple myeloma (RRMM)
 
	
 
Dose-limiting toxicities (DLTs), treatment-emergent adverse events, treatment-related adverse events, and changes in vital signs, electrocardiograms (ECGs), and clinical laboratory tests
 

Key Secondary	

 
Estimate overall response rate (ORR) and duration of response (DOR) of AMG 420 in subjects with RRMM
 
	
 
ORR
 
DOR
 

 
Evaluate the rate of minimal residual disease (MRD)-negativity at the time of CR
 
	
 
MRD negativity at the time of CR
 

Secondary	

 
Establish the safety and tolerability of AMG 420 in subjects with extramedullary relapsed multiple myeloma
 
	
 
DLTs, treatment-emergent adverse events, treatment-related adverse events, and changes in vital signs, ECGs, and clinical laboratory tests
 

 
Characterize the pharmacokinetics (PK) of AMG 420 when administered as 4-week continuous intravenous (cIV) infusion
 
	
 
AMG 420 PK parameters including, but not limited to, half-life (<math>t_{1/2}</math>), clearance, and apparent <math>C_{ss}</math>
 

Objectives	Endpoints
Secondary	

• Evaluate other measures of anti-myeloma activity of AMG 420 in subjects with RRMM:

– Time to response

– Progression-free survival (PFS)

– Overall survival (OS)

– Best overall response (BOR)

	

• Efficacy parameters according to International Myeloma Working Group (IMWG) response criteria, per investigator assessment:

– Time to response

– PFS

– OS

– BOR

Objectives	Endpoints
Exploratory	

---

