#### 10.4.2.2 Efficacy Analyses

Endpoint	Statistical Analysis Methods
Primary	Not applicable for phase 1b.
Secondary	
Tabular summaries of efficacy endpoints will be reported separately by dose level and part.
 
For subjects included in the Safety Analysis Set, the proportion of subjects with BOR of PR or better per IMWG and MRD negativity at the time of CR will be calculated and tabulated. DOR and time to response analyses will be done for subjects who are in Safety Analysis Set and have a best overall response of PR or better. The percentage of subjects with extended TFI of 4 weeks at approximately 6 months and 4 weeks or 8 weeks at approximately 12 months, out of all treated subjects and out of those who are eligible based on response status (only patients with MRD-negative CR at these landmark times are eligible for the extended TFI calculation). If appropriate, KM proportions at select time points, KM quartiles (when estimable) and KM curves will be provided for DOR, PFS, and OS. Descriptive statistics including median and range will be provided for time to response. Listings will be produced for all subjects indicating the MRD negativity, OS, PFS, time to response, and DOR.

Exploratory	Will be described in the statistical analysis plan finalized before database lock

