#### 10.4.2.3 Safety Analyses

##### 10.4.2.3.1 Analyses of Primary Safety Endpoint(s)

Endpoint	Statistical Analysis Methods
Primary	
The primary endpoints are safety endpoints. Unless otherwise specified, statistical analyses on safety endpoints will be done using subjects from the Safety Analysis Set, which includes subjects that are enrolled and received at least 1 dose of AMG 420. Descriptive statistics for safety endpoints will be tabulated overall and by dose level and part.
 
Adverse Events
 
Subject incidence of all treatment-emergent adverse events will be tabulated by system organ class and preferred term. The number and percentage of subjects reporting adverse events will be evaluated overall and by AMG 420 dose level and part will also be tabulated by relationship to AMG 420.
 
Tables of adverse events, fatal adverse events, serious adverse events, adverse events leading to withdrawal from investigational product or other

Endpoint	Statistical Analysis Methods

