	
protocol-required therapies, and significant treatment-emergent adverse events will also be provided.
 
Dose Limiting Toxicities
 
The analysis of the probability of DLTs will include data from DLT-evaluable subjects (see Section 7.4.1 for definition of DLT-evaluable). The primary analysis will only include DLTs that occur within the first cycle. If DLTs occur outside the first cycle, a sensitivity analysis will be performed where DLTs occurring outside of the specified time interval are included. The number and percentage of subjects reporting DLTs will be evaluated overall and by AMG 420 dose level and part.
 
Clinical Laboratory Tests
 
Clinical chemistry, hematology, and urinalysis data will be listed and reviewed for each subject. Values outside the normal laboratory reference ranges will be flagged as high or low on the listings. Depending on the size and scope of changes in laboratory data, the analyses of safety laboratory endpoints will include summary statistics over time and/or changes from baseline over time. Maximum shifts in grades of selected safety laboratory values between baseline and the worst on-study value may be tabulated.
 
Vital Signs
 
Vital signs data will be listed and reviewed for each subject. Depending on the size and scope of changes, the analyses of vital signs may include summary statistics over time and/or changes from baseline over time.
 
Electrocardiograms
 
Summaries over time and/or changes from baseline over time will be provided for all ECG parameters. Subjects' maximum change from baseline in QTcF will be categorized and the number and percentage of subjects in each group will be summarized. Subjects' maximum post baseline values will also be categorized and the number and percentage of subjects in each group will be summarized. All on-study ECG data will be listed, and select parameters of interest may be plotted.

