9.7.5 Analyses of Biomarker Endpoints

The analysis of Biomarker will be described and performed by Clinical Biomarker Group.

10. Changes From Protocol-specified Analyses

There are no changes to the protocol-specified analyses.

11. Literature Citations / References

12. Prioritization of Analyses

No Priority of outputs planned for this study

13. Data Not Covered by This Plan

The analysis of Biomarkers (except MRD) is not covered in this plan.

14. Appendices

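### SAP 9.6.6 leaves out the protocol's categorised maximum QTcF change from baseline, part of the primary safety analyses, while SAP Section 10 declares no changes

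*SAP*

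**What the plan says.** **Protocol.** Section 4.1 lists ECG change within the primary endpoint: "treatment-related adverse events, and changes in vital signs, electrocardiograms (ECGs), and clinical laboratory tests". The analysis table in 10.4.2.3.1 opens its primary row with "The primary endpoints are safety endpoints". Under electrocardiograms, that row asks for four things:

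- by-visit summaries of ECG parameters;
- a categorised change table, in which subjects' "maximum change from baseline in QTcF will be categorized and the number and percentage of subjects in each group will be summarized";
- a second categorised table, in which subjects' "maximum post baseline values will also be categorized and the number and percentage of subjects in each group will be summarized";
- a listing of all on-study ECG data.

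**SAP.** Section 9.6.6 has two sentences. The first is "Summaries over time and/or changes from baseline over time will be provided for all ECG parameters". The second covers absolute values only: subjects' "maximum post baseline values will be categorized and the number" and percentage in each group follow. Section 5 defines the averaged triplicate baseline ECG, the Fridericia formula and change from baseline. Section 9.1 says that descriptive statistics for continuous data include means, medians, standard deviations and ranges. Section 10 states: "There are no changes to the protocol-specified analyses".

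**The concern.** The dropped table is the only ECG output in the protocol that must report change from baseline. The by-visit sentence has the same and/or wording in both documents. In the protocol this does no harm, because the categorised maximum change is required in any case. In the SAP that requirement is gone, and a programmer could meet 9.6.6 with absolute values alone.

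The primary endpoint is worded in terms of change. With about 10 subjects per dose level, how many subjects had a given maximum QTcF change is the natural subject-level result, and the SAP as written does not produce it. The Section 10 statement compounds this: a reader relying on it would not know that a planned primary safety summary had gone.

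**Working it through.** The plan gives no figure on this point, so the check is a comparison of texts, followed by small illustrations of what each output can show.

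**1. ECG outputs side by side**

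| Output | Protocol 10.4.2.3.1 | SAP 9.6.6 |
|---|---|---|
| By-visit values and/or changes | Yes | Yes, same wording |
| Maximum QTcF change, categorised | Yes | Absent |
| Maximum post-baseline value, categorised | Yes, in addition | Yes |
| Listing of all on-study ECG data | Yes | Not repeated |

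SAP 9.6.6 shows no blacked-out text, so the absence is not an effect of redaction. The definitions needed for the missing table are all in SAP Section 5, but no visible section uses them for a categorised change.

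**2. What by-visit summaries would show, if change is summarised**

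Assume 10 subjects at a dose level and a +60 ms change in one subject at a visit, with the other nine unchanged. Neither document gives the 60 ms figure; it is an illustration.

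- Visit mean change: 60 / 10 = 6 ms.
- Visit range: 0 to 60 ms, so the large change is visible as the maximum.
- Category table: 1 / 10 = 10% of subjects.

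**3. What they would not show**

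Now take three visits, each with exactly one subject at +60 ms and nine at 0.

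- Case A, the same subject each time: maximum change of 60 ms in 1 / 10 = 10% of subjects.
- Case B, a different subject each time: maximum change of 60 ms in 3 / 10 = 30% of subjects.

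In both cases every visit row has the same mean (6 ms), median (0), standard deviation and range (0 to 60 ms). The by-visit output cannot separate 10% from 30%. The categorised maximum change does.

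**4. Whether the retained table can stand in**

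Assume a subject who moves from 390 to 455 ms. The change is 455 − 390 = 65 ms, yet the maximum value stays below 470 ms, the baseline limit in exclusion criterion 213. Neither document states category limits, so where this subject would fall is open. The example shows only that a large change and a modest absolute value can occur together.

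**5. Version check**

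SAP Section 1 says it implements Amendment 4 (20 May 2020). The available protocol is Amendment 5 (17 September 2021). The Amendment 5 rationale names 10.2.1 as the only Section 10 entry among its changes, and 10.4.2.3.1 is not listed.

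**The case against.** **A reader might infer that an individual prolongation would be averaged away.** The documents do not support that. SAP 9.1 promises ranges, so if change is summarised by visit, the subject at +60 ms appears as that visit's maximum and not only as a 6 ms shift in the mean. This narrows the loss to the count of subjects by maximum change across visits. The reassurance is itself conditional, because the and/or wording does not oblige anyone to summarise change.

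**Individual data can be read from listings.** The protocol requires all on-study ECG data to be listed, cohorts are small, and ECGs are required only in cycles 1 and 2. The protocol commitment stands although SAP 9.6.6 does not repeat it. A listing lets a reader reconstruct the counts by hand, but it is not the planned summary.

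**The Section 10 statement refers to Amendment 4.** That text was not available, so the mismatch is shown only against Amendment 5. The Amendment 5 change list makes a version explanation unlikely but does not exclude it.

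**A reader might also infer that the SAP dropped the extended treatment-free-interval percentages.** Protocol 10.4.2.2 includes "The percentage of subjects with extended TFI of 4 weeks at approximately 6 months" in its secondary row, and the visible SAP uses the term only in its abbreviation list. That is not enough to show an omission. The exploratory endpoint row in SAP 2.1 is blank and SAP 9.5.3 has a heading without text, so the analysis may sit in removed material. The measure is also absent from the visible secondary endpoints in protocol 4.1.

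**Conclusion.** The point holds as a minor mismatch between protocol and SAP. A categorised summary that the protocol places in its primary safety analyses is absent from SAP 9.6.6, and the no-changes statement in Section 10 does not match the available protocol. The SAP also guarantees no ECG change-from-baseline output, although the primary endpoint includes ECG change.

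The size is one missing table. Under the assumed values above, by-visit output could not tell 10% of a 10-subject cohort from 30%. That shows what is lost and does not forecast any result.

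The conclusion rests on the visible text of SAP 9.6.6 and on the assumption that Amendment 4 carried the same ECG paragraph as Amendment 5. It does not extend to the treatment-free-interval percentages.

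**What to change.** In SAP 9.6.6, restore the number and percentage of subjects by category of maximum QTcF change from baseline, by dose level and overall. Use the QTcF, triplicate-baseline and change definitions already in SAP Section 5, and state the category limits in advance. Make the by-visit change summary definite by removing the and/or choice. Correct the Section 10 statement; if the table is left out on purpose, Section 10 should say so and give the reason.

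The cost is one extra table from data already collected, plus a short text edit. Separately, the sponsor should confirm that the treatment-free-interval analysis in protocol 10.4.2.2 is covered somewhere in the full SAP.

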9.6.8 Exposure to Investigational Product

The average dose administration (μg), cumulative dose (μg), number of cycles, duration of treatment, number and percentage of subjects with dose modifications, reasons for modification will be summarized using descriptive statistics. Subject-level data may be provided instead of the summary if the subject incidence is low or single dose is given.

Descriptive statistics will be produced to describe the exposure to investigational product by treatment group.

Extent of exposure to study treatments will be summarized for Safety population

- Duration of treatment (days)
 - Defined as the duration (in weeks) from the date of the first dose to the date of the last dose of study drug + 1
- Total number of treatment cycles started
 - Defined as the total number of treatment cycles in which at least one dose of study drug is administered.
- Cumulative dose received of AMG420 across all cycles, defined as the cumulative dose of AMG 420.
- Average dose of AMG420, defined as the total dose received divided by the number of days on treatment administered .

9.6.9 Exposure to Concomitant Medication

Number and proportion of subjects receiving therapies of interest will be summarized by preferred term for each treatment group as coded by the World Health Organization Drug dictionary.

9.7 Other Analyses

9.7.1 PK Analyses

The PK parameters of AMG 420 including, but not limited to, average C_{ss} , clearance, and half-life ($t_{1/2}$) for serum AMG 420 will be estimated using non-compartmental methods and summarized by dose level using means, geometric means, standard

deviations, coefficients of variation, medians, minimums, and maximums. Individual concentration-time profiles will be summarized by dose level. Plasma AMG 420 concentrations at each time point along with PK parameter values may be listed for each subject. Summary statistics will be computed for each sampling time and parameter as appropriate. The relationship between AMG 420 exposure and efficacy/safety may be conducted.

9.7.2 Analyses of Pharmacokinetic or Pharmacokinetic/Pharmacodynamic Endpoints

PK/PD analyses will be provided by the Department of Clinical Pharmacology, Modeling & Simulation (CPMS). Actual collection times of PK samples will be recorded to assess the plasma concentration. The PK parameter estimates for AMG420 will be summarized. Exploratory analyses may be performed to evaluate the relationship between the estimated PK parameters and selected safety, biomarker, or clinical effect endpoints. In addition, the population modeling program may be used to fit a nonlinear mixed effects model to estimate PK parameters. Details regarding the analyses will be provided in a separate analysis plan by CPMS.

9.7.3 Analyses of Clinical Outcome Assessments

Analysis of clinical outcome assessments is not planned for this study.

9.7.4 Analyses of Health Economic Endpoints

Analyses of Health Economic Endpoints are not planned for this study.

9.7.5 Analyses of Biomarker Endpoints

The analysis of Biomarker will be described and performed by Clinical Biomarker Group.

10. Changes From Protocol-specified Analyses

There are no changes to the protocol-specified analyses.

11. Literature Citations / References

12. Prioritization of Analyses

No Priority of outputs planned for this study

13. Data Not Covered by This Plan

The analysis of Biomarkers (except MRD) is not covered in this plan.

14. Appendices

Appendix A. Reference Values/Toxicity Grades

The Common Terminology Criteria for Adverse Events (CTCAE) v5.0 is available at the following link:

http://ctep.cancer.gov/protocolDevelopment/electronic_applications/ctc.htm

Technical Detail and Supplemental Information Regarding Statistical Procedures and Programs

Imputation Rules for Partial or Missing Stop Dates

If the month and year are present, impute the last day of the month. If only the year is present, impute December 31 of that year. If the stop date is entirely missing, assume the event or medication is ongoing.

Imputation Rules for Partial or Missing Start Dates

		Stop Date						
		Complete: yyyymmdd		Partial: yyyyymm		Partial: yyyy		
Start Date		<1 st Dose	≥1 st Dose	<1 st Dose yyyyymm	≥1 st Dose yyyyymm	<1 st Dose yyyy	≥1 st Dose yyyy	Missing
	Partial: yyyyymm	=1 st Dose yyyyymm	N/A	1	N/A	1	N/A	
≠ 1 st Dose yyyyymm		2		2	2	2	2	2
Partial: yyyy	=1 st Dose yyyy	N/A	1	N/A	1	N/A	1	1
	≠ 1 st Dose yyyy		3		3	3	3	3
Missing		4	1	4	1	4	1	1

- 1 = Impute the date of first dose
- 2 = Impute the first day of the month
- 3 = Impute January 1 of the year
- 4 = Impute January 1 of the stop year

Note: For subjects who were never treated (first dose date is missing), partial start dates will be set to the first day of the partial month.

Note: If the start date imputation leads to a start date that is after the stop date, then do not impute the start date.

Imputation rules for stop date:

For partial stop date mmyyyy, impute the last day of the month.

For partial stop date yyyy, impute December 31 of the year.

For completely missing stop date, do not impute.

If the stop date imputation leads to a stop date that is after the death date, then impute the stop date as the death date.

If the stop date imputation leads to a stop date that is before the start date, then there is a data error and do not impute the stop date. (ie. set the stop date as missing).

Code Fragments:

Provisional Code Fragments for calculating a confidence interval using the Clopper Pearson Method. The following example SAS code will be utilized for the response rate analysis providing the proportion of subjects responding to treatment with corresponding 80% confidence intervals.

```
data propci (keep = ns p low_ci upp_ci);  
n=xx; * total n within the treatment group;  
do ns= xx; *number of responders;  
p=ns/n; * response rate;  
q=1-p;  
lowF=FINV(0.1, 2*ns, 2*(n-ns+1)); /* use for 2-sided 80% CI */  
UppF=FINV(1-0.1, 2*(ns+1), 2*(n-ns)); /* use for 2-sided 80% CI */  
low_ci = 1 / (1+(n-ns+1) / (ns*lowf)); * lower CI for response rate;  
upp_ci = 1 / (1+(n-ns) / ((ns+1)*uppf)); *upper CI for response rate;  
if p=1 then upp_ci=1;  
if p=0 then low_ci =0;  
output;  
end;run;
```

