2.2 Hypotheses and/or Estimations

The ORR according to IMWG response criteria along with 95% CI will be calculated per **investigator** assessment for subjects with RRMM. The lower bound of the binomial 2-sided 95% confidence interval for ORR not lower than 35% is considered clinically meaningful.

3. Study Overview

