9.1 General Considerations

Descriptive statistics will be provided for selected demographics, safety, PK, pharmacodynamic and biomarker data by dose, dose schedule, and time as appropriate. Descriptive statistics on continuous data will include means, medians, standard deviations and ranges, while categorical data will be summarized using frequency counts and percentages. Time to event endpoints will be summarized with Kaplan-Meier (KM) proportions at select time points, KM quartiles (when estimable), the number of

subjects with events, the number of subjects censored, and censoring reasons. Duration of follow-up for time to event endpoints will be estimated using the reverse Kaplan Meier method (Schemper and Smith, 1996). Point estimates for efficacy endpoints will be accompanied by 2-sided 95% confidence intervals including KM quartiles (Klein and Moeschberger, 1997), KM proportions (Kalbfleisch and Prentice, 1980), and binomial proportions (Clopper and Pearson, 1934). Graphical summaries of the data may also be presented.

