9.5 Efficacy Analyses

9.5.1 Analyses of Key Secondary Efficacy Endpoint(s)

9.5.1.1 Overall Response Rate

The number (%) of subjects with a best overall response of sCR, CR, VGPR, PR, MR, SD, PD or IE will be summarized.

Overall response rate is defined as the proportion of subjects for whom the best overall response is sCR, CR, VGPR, or PR as determined by International Myeloma Working Group Uniform Response Criteria (IMWG-URC). The ORR along with the associated 95% exact binomial confidence interval (Clopper-Pearson method) will be determined.

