9.5.1.3 MRD Negativity at CR

MRD negativity analysis will be performed for all subjects included in the safety analysis set. Number of MRD[-] responders at CR along with exact 2-sided 95% will be provided by using Clopper & Pearson method

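### The SAS code in SAP Appendix A for the response rate gives 80% confidence limits, but the plan requires 95%

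*SAP*

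**What the plan says.** **Sections that require 95%**

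- SAP 9.5.1.1 sets both level and method for ORR: "The ORR along with the associated 95% exact binomial confidence interval (Clopper-Pearson method) will be determined".
- SAP 9.1 sets the general rule: "Point estimates for efficacy endpoints will be accompanied by 2-sided 95% confidence intervals including KM quartiles", and it names Clopper-Pearson for binomial proportions. Protocol 10.4.2.1 has the same rule.
- SAP 2.2 and protocol 4.2 tie the efficacy benchmark to that level: "The lower bound of the binomial 2-sided 95% confidence interval for ORR not lower than 35% is considered clinically meaningful".
- SAP 9.5.1.3 asks for the same level and method for MRD negativity.

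**Where 80% appears**

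Only the code fragment in SAP Appendix A mentions 80%. It is headed as provisional and called an example, yet its introduction reads: "following example SAS code will be utilized for the response rate analysis providing the proportion of subjects responding to treatment with corresponding 80% confidence intervals". The level is stated again in the comments on both limit lines and is hard-coded in both, for example "UppF=FINV(1-0.1, 2*(ns+1), 2*(n-ns)); /* use for 2-sided 80% CI".

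SAP section 10 states: "There are no changes to the protocol-specified analyses".

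**The concern.** The appendix and the body of the SAP give different confidence levels for the same estimate, and the SAP has no rule for which prevails. The 80% level is not a lone misprint: the sentence, both comments and both constants agree on it. The only blanks for the programmer to fill are the sample size and the number of responders. Completing the fragment as instructed therefore yields 80%.

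An 80% interval presented as the planned one would overstate the precision of ORR. The error also runs in the favourable direction. The 35% benchmark is written for the lower limit of a 95% interval, and an 80% lower limit is higher, so fewer responders are needed to reach it.

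**Working it through.** **Inputs**

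- Tail probability in the code: 0.1 for each limit (SAP Appendix A).
- Required level: two-sided 95%, so 0.025 in each tail (SAP 2.2, 9.1, 9.5.1.1; protocol 4.2, 10.4.2.1).
- Benchmark: lower limit not below 35% (SAP 2.2, protocol 4.2).
- Sample size: about 10 per dose level and about 20 in total (protocol 10.1).

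**Formulas as printed**, with n subjects, x responders, tail probability a, and F(p; d1, d2) the p-quantile of the F distribution:

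- Lower = 1 / (1 + (n − x + 1) / (x · F(a; 2x, 2(n − x + 1))))
- Upper = 1 / (1 + (n − x) / ((x + 1) · F(1 − a; 2(x + 1), 2(n − x))))

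**Step 1: what level does the code produce?** For every x at n = 10 and n = 20, the printed formulas with a = 0.1 match the exact 80% Clopper-Pearson limits from beta quantiles (largest difference about 1e-16). With a = 0.025 they match the exact 95% limits equally closely. The formula is correct, and only the tail probability is wrong.

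**Step 2: one case in full, 6 of 10**

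- a = 0.1: F(0.1; 12, 10) = 0.4571, so Lower = 1 / (1 + 5 / (6 × 0.4571)) = 35.4%. F(0.9; 14, 8) = 2.475, so Upper = 1 / (1 + 4 / (7 × 2.475)) = 81.2%. Width 45.8 points.
- a = 0.025: F(0.025; 12, 10) = 0.2964, so Lower = 1 / (1 + 5 / (6 × 0.2964)) = 26.2%. F(0.975; 14, 8) = 4.130, so Upper = 1 / (1 + 4 / (7 × 4.130)) = 87.8%. Width 61.6 points.
- Ratio 45.8 / 61.6 = 0.744, so the printed interval is 26% narrower.

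The same steps for 11 of 20 give 38.5% to 70.7% as printed and 31.5% to 76.9% at 95%, which is 29% narrower.

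**Step 3: fewest responders with a lower limit of at least 35%**

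| n | 95%, as planned | Code as printed |
|---|---|---|
| 9 | 7 | 6 |
| 10 | 8 (lower limit 44.4%; 7 of 10 gives 34.75%) | 6 (35.4%) |
| 11 | 8 | 7 |
| 12 | 9 | 7 |
| 20, pooled | 12 (36.05%) | 11 (38.5%) |

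Rows other than n = 10 are included because cohort sizes are approximate and some subjects may be replaced.

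**Step 4: chance of reaching the benchmark if the true ORR is exactly 35%** (binomial upper tail at the counts in the table)

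- n = 10: P(X ≥ 6) = 9.5% with the printed code; P(X ≥ 8) = 0.5% with 95% limits.
- n = 20: P(X ≥ 11) = 5.3% with the printed code; P(X ≥ 12) = 2.0% with 95% limits.

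**The case against.** The best defence is that this would probably be caught. The fragment is labelled provisional and an example. SAP 9.5.1.1 is unambiguous on level and method. SAP 8.7 says that validated standard macros will be used where they can produce the output, and that output will be verified under risk-based quality control. An exact binomial interval may well be a standard output, though the SAP does not say so. Moreover, the primary endpoints are safety, ORR is descriptive, and the dose level review team works from safety, laboratory and PK data. A wrong conclusion on the benchmark needs two failures: the printed code is run, and its output is then compared with a benchmark that names 95%.

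These points stand as to likelihood and weight. They do not remove the contradiction, because the appendix says that the code will be used. A quality check against the appendix would confirm 80%, and a check against 9.5.1.1 would reject it.

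A second fair point concerns pooling. Protocol 10.4.2.2 reports efficacy separately by dose level, and the code takes its denominator within the treatment group. Neither document says that the 35% benchmark applies to both cohorts together, so the n = 20 figures are illustrative.

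**Conclusion.** The concern holds. As printed, the Appendix A code gives exact two-sided 80% limits for an estimate that both documents require at 95%, and nothing in the plan authorises the lower level.

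The certain effect of running it is intervals about 26% too narrow at n = 10 (1 to 9 responders) and about 29% too narrow at n = 20. The effect on the benchmark is conditional: only if the 80% limit is compared with 35% would one or two fewer responders be needed, depending on the final cohort size. At exactly 10 per cohort, 6 or 7 responders would appear to reach the benchmark and would not at 95%. If both cohorts were pooled at exactly 20, the same is true of 11.

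This should be corrected before the analysis is programmed. It does not touch the primary safety analysis or any dosing or enrollment decision described in the documents.

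**What to change.** In SAP Appendix A, Code Fragments:

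- Replace 0.1 with 0.025 in both FINV calls, giving FINV(0.025, ...) for the lower limit and FINV(1-0.025, ...) for the upper.
- Change 80% to 95% in the introductory sentence and in both code comments.

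Nothing else in the SAP needs to change on this point. Responder counts should not be written in as thresholds, because the cohort sizes are approximate.

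The cost is two constants, one sentence and two comments, with no effect on data collection or sample size. Reported intervals will be wider than the printed code would give, which is the width that the plan already requires.
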